Aims 1-4	Medical cannabis use	Initial soft-gel capsule dispensed at Vireo Certification for medical cannabis (date, doctor, conditions) All medical cannabis products dispensed (date, product, dose, amount dispensed) Self-reported medical and unregulated cannabis use (product, # of days used, route, dollar amount of unregulated cannabis purchased, ASI)	PR MR PR TQ
Primary outcome variables			
Aims 1, 4	Pain Severity	Brief Pain Inventory (BPI) Severity subscale ⁹⁰	TQ
Secondary outcome variable			
Aims 2, 4	Inflammatory cytokines	Pro-inflammatory cytokines (TNF α , IL-6) Anti-inflammatory cytokines (IL-4, IL-10)	B B
Aims 3, 4	Adverse events	VL, CD4 count AIDS Clinical Trial Group (ACTG Adherence) ⁹³ , Visual Analog Scale (VAS) ⁹⁴ ARVs dispensed Depression (Center for Epidemiological Studies-Depression Scale [CES-D])), Generalized Anxiety Disorder (GAD-7) ⁹⁶	B IQ PR IQ
Other measures			
Aims 1-4	Sociodemographics	Age, race/ethnicity, education, insurance, sex, gender	IQ
Aims 1-4	Pain characteristics	Brief Pain Inventory (BPI) Interference subscale ⁹⁰ Pain catastrophizing scale ⁹⁸ , Pain DETECT questionnaire ⁸⁴	IQ IQ
Aims 1-4	Pain treatment	Pain treatment (SSRIs, gabapentin, injections, physical therapy)	IQ/MR/PR
Aim 3	Substance use/disorder	Smoking (Fagerstrom test for nicotine dependence) ⁹⁹ , Alcohol Use Disorders Identification Test (AUDIT) ¹⁰⁰ , ASI ⁹⁷	IQ
Aim 3	HIV Risk Behaviors	HIV risk behaviors (HIV Risk-taking Behavior Scale ¹⁰¹⁻¹⁰³)	IQ
Aims 3, 4	Psychiatric symptoms	PTSD Checklist (PCL), ¹⁰⁴ Insomnia severity index, ¹⁰⁵	IQ
Aims 1, 3, 4	Quality of Life	Roland Morris Disability Questionnaire ¹⁰⁶ , Patient Reported Outcomes Quality of Life-HIV (PROQOL-HIV) ¹⁰⁷	IQ
Aims 1-4	Medical comorbidities	Comorbidities (obesity, cardiovascular disease, diabetes)	MR
Aims 1-4	Side effect vs benefit	Treatment Satisfaction Questionnaire for Medication (TSQM-9) ⁹¹	TQ
Aims 1-4	Urine cannabinoid	Urine GCMS for cannabinoids	

B=blood test; MR=Medical records; PR=Pharmacy records or Prescription Monitoring Program; IQ= in-person questionnaire; TQ=phone questionnaire; SSRI=selective serotonin reuptake inhibitor; TQ measures occur every week; IQ occurs at 0 and 14 weeks. B occurs at 0 at 14 weeks.

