In-person visits: Participant's 2 in-person visits will occur in private rooms at the Montefiore/Einstein ICTR Clinical Research Center. At the baseline visit, study staff will describe the study and obtain written informed consent. Tracking forms as well as agreements to release medical, pharmacy, and PMP records will be completed. Participants will receive a refillable debit card for compensation. At all in-person visits, we will administer questionnaires, and collect blood and urine samples. Participants will receive \$27.50 for each in-person visit.

Phone or web visits will occur weekly over 14 weeks and include brief (5-7 minute) questionnaires administered by study staff over the phone or completed on-line. A total of 15 visits will occur, the first at baseline, when participants can be trained on how to complete it, and then one at the end of each week of the follow-up period. Participants will receive \$3 on debit cards after completing each phone or web-based questionnaire.

Blood draws will occur at week 0 and 14 in-person visits. They will measure VL, CD4 count, pro- and anti-inflammatory cytokines. Participants will be compensated an additional \$15 for each visit in which there is a blood draw.

Main independent variable will be the soft gel capsule product dispensed at Vireo, including a 1) high THC capsule, or 2) high CBD capsule. Other key independent variables will be cumulative THC and CBD taken (weeks 3-14, continuous measures).

Main outcome variables: Our primary outcome is pain severity, measured via the BPI severity scale (ordinal variable), as recommended by a committee of international pain experts.⁹² It is an 11-point (0-10) numerical rating scale of pain intensity, where 0 is 'No pain' and 10 is 'Pain as

bad as you can imagine'. Participants will complete the BPI severity scale in each phone visit (baseline and at each weekly visit).

Pro- (TNF α , IL-1 β , IL-6) and *anti-* (IL-4, IL-10) *inflammatory cytokines (secondary outcomes;* 0, 14 week *blood draws*) will be measured with Luminex assay and reported as picograms per mm 3 (continuous measure).

Adverse events (secondary outcomes) will be ARV adherence (AIDS Clinical Trial Group [ACTG] Adherence Interview,^{93,108} Adherence Visual Analog Scale [VAS; weekly]),⁹⁴ VL suppression (blood draws at 0, 14 weeks; copies/mL); and psychological symptoms—depression (CES-D; 0 and 14 weeks),⁹⁵ anxiety (GAD-7; 0 and 14 weeks),^{96,94,97,109}

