Aim 3: Examine how medical cannabis use affects adverse events. *H4: Participants who use high THC (vs. high CBD) cannabis products will have more psychological symptoms, poorer ARV adherence, and less suppressed VL.* We will examine whether participants using high THC products vs high CBD products have a greater chance of adverse events, including psychological symptoms, ARV adherence, and VL. We will use mixed-effects linear regression analysis for continuous measures (VL, ARV adherence, and psychological symptoms). Each adverse event (Table 8) will be included in a separate model. We will repeat this model using alternative measures of medical cannabis (cumulative dose of THC and CBD).

Aim 4: Explore mechanisms by which medical cannabis promotes analgesia. *H5: Different doses of THC and CBD will have differing effects on inflammatory cytokines, psychological symptoms, and ultimately analgesia.*

We will use a pooled analysis of THC and CBD, using weekly questionnaires and PMP records. We will examine these relationships longitudinally in a stepwise process. First, we will conduct a mixed-effects model to examine how potential mediators lead to analgesia (reduction in BPI severity score). We will repeat analyses for possible mediators, including inflammatory cytokines and psychological symptoms. We will also determine if exposures influence changes in these variables over time, which in turn, influence change in analgesia (e.g., using time-lagged mediators and outcomes). Mediators found to be significant will be included in the final model.⁹² We will calculate the standardized total effect from the exposures to analgesia as well as the standardized mediational (i.e., indirect) effects via mediators. The mediational effect is calculated as the product of the effect from the exposures to the mediators, and the effect from the mediators to the outcome.

8) Data quality control and database management

Data management: Questionnaire, medical records, and PMP data will be de-identified and entered by study staff into a password-protected computer and database. Paper records will be stored in a locked filing cabinet that only research staff can access. Medical and PMP record data will be de-identified and entered in a secure HIPAA compliant web-based system. To protect confidentiality, we will use separate processes for ID- and name-based files and seek a certificate of confidentiality.

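### Aim 4's time-lagged mediation cannot be run: cytokines, CES-D and GAD-7 are measured only at weeks 0 and 14, so no post-exposure mediator value precedes a later pain score

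*Combined protocol and SAP*

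**What the plan says.** Section 7.A, Aim 4, names inflammatory cytokines and psychological symptoms as candidate mediators. It plans to test whether exposure changes them over time and whether those changes then alter analgesia, giving "using time-lagged mediators and outcomes" as the example method. The next commitment carries no such qualifier: "We will calculate the standardized total effect from the exposures to analgesia as well as the standardized mediational (i.e., indirect) effects via mediators". The estimator is also fixed: "The mediational effect is calculated as the product of the effect from the exposures to the mediators", multiplied by the mediator-to-outcome effect.

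The schedule is in section 2.C:

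- The footnote to the measures table reads "TQ measures occur every week; IQ occurs at 0 and 14 weeks. B occurs at 0 at 14 weeks". The table codes CES-D and GAD-7 as in-person questionnaires (IQ), cytokines as blood tests (B) and BPI severity as a phone questionnaire (TQ).
- The text agrees: "Blood draws will occur at week 0 and 14 in-person visits"; "depression (CES-D; 0 and 14 weeks"; "anxiety (GAD-7; 0 and 14 weeks".
- BPI severity is collected at baseline and at each weekly contact, "one at the end of each week of the follow-up period". That makes 15 scores, the last at week 14.

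The Aim 2 text in section 7.A and the phlebotomy paragraph in section 6.A give the same two time points for cytokines and blood.

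**The concern.** A lagged mediation analysis needs a mediator value taken after exposure has begun and before the pain score it is meant to explain. The schedule seems to provide none. If so, the one device the plan offers for putting mediator change before pain change is unavailable, while the indirect effect would still be calculated.

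The stake is the direction of the mechanism finding. Pain relief may well improve mood or lower cytokines; the protocol's background describes pain and psychological symptoms as closely interrelated without settling which comes first. If pain leads and the mediator follows, the planned product would still be read as dose relieving pain through mood or cytokines, and the week 0 and week 14 data would not reveal the error.

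**Working it through.** The plan gives no sample size, power or effect figure for Aim 4, so there is nothing to reproduce first.

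**1. Pair count (documents only).** BPI weeks are 0 to 14 and mediator weeks are 0 and 14. Week 0 counts as pre-exposure because the eligibility criteria require no medical cannabis dispensed in the previous 60 days or used in the previous 30.

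| Ordering | Pairs per participant |
|---|---|
| Post-exposure mediator before a later BPI score | 0 |
| Post-exposure mediator and BPI in the same week (14, 14) | 1 |
| Post-exposure BPI before a later mediator (weeks 1–13, then 14) | 13 |
| Baseline mediator before a later BPI score | 14, but the mediator precedes exposure |

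If exposure is counted from week 3, where the cumulative-dose variable starts, the third row becomes 11 (weeks 3–13) and the first stays 0. The only post-exposure lag available is the reverse of the planned one.

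**2. What the remaining data can distinguish.** With dose X, mediator M and pain Y, there are three correlations. The chain X→M→Y with a direct X→Y path has three free paths, and so does X→Y→M with a direct X→M path. Each reproduces the three correlations exactly, so fit cannot choose between them.

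**3. Size of a possible error (assumed inputs).** Suppose dose acts on pain with standardised effect c, the mediator follows pain with correlation r, and there is no other path. True mediation is then zero.

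- Dose-to-mediator effect: a = r·c.
- Mediator-to-pain effect adjusted for dose: b = (r − c·rc)/(1 − r²c²) = r(1 − c²)/(1 − r²c²).
- Apparent share mediated: ab/c = r²(1 − c²)/(1 − r²c²).

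Example with r = 0.5, c = 0.2: 0.25 × 0.96 / (1 − 0.01) = 0.24/0.99 = 0.242.

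| c | r = 0.3 | r = 0.5 | r = 0.7 |
|---|---|---|---|
| 0.2 | 0.087 | 0.242 | 0.480 |
| 0.3 | 0.083 | 0.233 | 0.466 |
| 0.4 | 0.077 | 0.219 | 0.447 |
| 0.5 | 0.069 | 0.200 | 0.419 |

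**4. Illustrative simulation (all inputs assumed except the sample size).** The setting was 84 participants (the plan's 42 per arm), 1000 cohorts per setting, weekly carry-over 0.6, dose effect 0.5 SD, path strength 0.3, 0.5 or 0.7, dose either fixed or responding to the previous week's pain with pain-related stopping, and score reliability 1.0 or 0.85. The week 0/14 product of effects was called significant (both paths p < 0.05) in 8–61% of cohorts when mood only followed pain, and in 27–58% when mood truly drove pain. The ranges overlap, so a significant product says little about direction.

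**The case against.** The strongest reply is that the lag is introduced as an example, in an aim headed as exploratory, and that a change-on-change product from weeks 0 and 14 can still be fitted. Both points are true. They show that an estimate can be computed, not that it can be read as mechanism. The commitment to an indirect effect is unconditional, and no other device for establishing order is offered.

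A second reply is that BPI scores at weeks 1–13 are already collected and carry some information on direction. The week-14 mediator can be regressed on earlier pain, and the week-14 mediator–pain association can be adjusted for pain at weeks 12 and 13. This part stands, with a condition. In illustrative simulations with assumed inputs, the adjustment held false mediator-to-pain signals to 4–8% when the mediator followed pain with a one-week lag. It gave 44–93% when the mediator followed pain, or the two acted on each other, within the same week. The plan has no basis for assuming one lag over another, so the adjustment is a sensitivity analysis and does not identify direction.

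Third, section 3.C says the questionnaires cover psychological symptoms, which might suggest weekly collection. It describes in-person and phone questionnaires together and names no instrument or week, so it does not displace the explicit schedule for CES-D and GAD-7. The addiction severity instrument (ASI) cited for psychosis symptoms is listed in the measures table both in the cannabis-use row, which has a weekly source, and as an in-person measure. That is an ambiguity, and it does not touch the mediators counted here.

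Finally, the 7–48% figures depend on assumed correlations, on zero true mediation, and on single-time correlations without baseline adjustment. They show what could happen and are not estimates for this study.

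**Conclusion.** The concern holds. For cytokines, CES-D and GAD-7 the lagged mediator-to-pain step has 0 usable pairs, which follows from the documents alone. The planned product of effects would rest on a single same-week association whose direction the week 0 and week 14 data cannot determine. How misleading it would be depends on unknown correlations; under the assumptions shown, a mediator with no causal role could appear to carry between 7% and 48% of the dose effect.

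The reach is limited. Aim 4 is exploratory. The primary arm comparison, the dose-to-mediator change and the dose-to-pain association can all still be estimated, although the dose paths are observational and open to confounding by self-chosen intake. The change should be made, but it does not bear on the primary result.

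**What to change.** **(a) Wording change.** For mediators measured only at weeks 0 and 14, remove the time-lagged wording and do not report a mediational effect as mechanism. Report dose-to-mediator change and the change-on-change association with pain, labelled as same-time with direction unknown, and as observational for dose. The adjustment for week 12–13 pain can be added as a sensitivity analysis from existing data, with its dependence on the lag stated. The cost is text only; Aim 4 gives up its mediated-effect estimate for these mediators.

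**(b) Optional, for participants not yet past mid-study.** Add CES-D and GAD-7 to one or two existing mid-study weekly contacts, and test them against the next weekly BPI score adjusted for same-week BPI. One contact at week 7 would precede 7 BPI scores (weeks 8–14). Contacts at weeks 5 and 10 would give 9 + 4 = 13 mediator-before-pain pairs. No visit or blood draw is added, but contacts now planned at 5–7 minutes would lengthen by a few minutes (an assumption). The documents do not say how many participants could still contribute.

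Present (b) as a test of direction, not of the size of an indirect effect. In the simulation above, adjusted also for dose, it wrongly signalled mood-before-pain in 3.6–6.2% of cohorts with error-free scores and 5.4–11.2% at reliability 0.85. It detected a true mood-to-pain effect in 27–86% and 20–72% respectively. It does nothing for cytokines, for which (a) applies.

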The benefits of cannabis may be offset by its adverse events.²⁷ Cannabis is linked to psychological symptoms including anxiety, depression,²⁸ and psychotic symptoms.²⁹ In some studies, cannabis use is associated with poor ARV adherence and virologic failure;³⁰ in others, this is not the case.³¹ No studies have examined how THC/CBD content contributes to adverse events (psychological symptoms, poor ARV adherence, and virologic failure).

Our overarching goal is to test how medical cannabis use affects neuropathic pain, with particular attention to THC/CBD content and adverse events. We propose an observational cohort study of 100 PLWH with (a) neuropathic pain, (b) active certification for medical cannabis, and (c) intent of being dispensed soft-gel capsule products at a medical cannabis dispensary (including high THC: low CBD product and high CBD:low THC product). Over 14 weeks, participants will have 2 in-person visits and 15 phone-based questionnaires (one at baseline, and every week for 14 weeks). Data sources will be blood and urine samples, questionnaires, and medical and pharmacy records. The primary independent variable will be the type of soft-gel capsule product. The secondary independent variable will be reported cumulative THC and CBD dose. The primary outcome will be self-reported pain severity.³² Secondary outcomes will be pro-inflammatory cytokines (TNF α , IL-6), anti-inflammatory cytokines (IL-4, IL-10),¹⁵ psychological symptoms (symptoms of depression,³³ anxiety,³⁴ and psychosis³⁵), ARV adherence, and VL. Among PLWH with neuropathic pain, we will:

Aim 1: Examine how medical cannabis use affects self-reported pain. *H1:* The effect of medical cannabis use on self-reported pain-severity will differ by THC/CBD content.

Aim 2: Examine how medical cannabis use affects pro- and anti-inflammatory cytokines.

H2: Medical cannabis that has higher THC content will have greater reduction in pro-inflammatory cytokines (TNF α , IL-6). *H3:* Medical cannabis that has higher CBD content will have greater increase in anti-inflammatory cytokines (IL-4, IL-10).

Aim 3: Examine how medical cannabis use affects adverse events. *H4:* Participants who use high THC (vs. high CBD) cannabis products will have more psychological symptoms, poorer ARV adherence, and less suppressed VL.

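### Aim 4 carries only significant mediators into its final model and estimates indirect effects on the same participants, so small-to-moderate effects that pass are biased away from zero.

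*Combined protocol and SAP*

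**What the plan says.** Section 7.A, Aim 4, sets out a stepwise mediation analysis. In the first step, "we will conduct a mixed-effects model to examine how potential mediators lead to analgesia". The plan continues: "We will repeat analyses for possible mediators, including inflammatory cytokines and psychological symptoms". It next looks at whether the exposures change the mediators and, through them, pain, for example with time-lagged terms. Then comes the selection rule: "Mediators found to be significant will be included in the final model". Standardized total and indirect effects follow: "The mediational effect is calculated as the product of the effect from the exposures to the mediators", multiplied by the effect of the mediators on the outcome.

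The plan does not say which path must be significant, or at what level. The 5% two-tailed level appears only in the Aim 1 power calculation (section 3.A). For Aim 4 there is no multiplicity rule, split sample, shrinkage, resampling of the selection step, or statement on how unselected mediators will be reported. The aim is labelled exploratory: "Explore mechanisms by which medical cannabis promotes analgesia".

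**The concern.** When the same data choose a mediator and estimate its effect, the mediator is kept partly because its estimate happened to be large. The product that defines the indirect effect inherits that excess. An interval computed as if the mediator had been fixed in advance lacks its stated coverage.

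At stake is how the mechanism results are read. Section 1.A names the unknown mechanism of analgesia as a gap the study should fill, and later studies would be planned around these indirect effects.

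**Working it through.** **No figure to reproduce.** The documents give no power, effect size or error rate for Aim 4.

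**Inputs from the documents**
- 100 recruited, 15% attrition, 42 per arm (section 3.A): 2 × 42 = 84 in the pooled analysis.
- At least six candidate mediators: TNF-α, IL-6, IL-4 and IL-10 (section 1.A), CES-D and GAD-7 (section 2.C). Section 2.C also lists IL-1β, which would make seven.
- Cytokines, CES-D and GAD-7 are measured only at weeks 0 and 14.

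**Assumptions, not in the documents:** one mediator; a single-level linear model; exposure-mediator effect a = 0.25 SD; mediator-pain effect b = 0.15 to 0.30 SD; screen at two-sided 5%.

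**Hand check, one-path screen, b = 0.20**
- SE ≈ 1/√84 = 0.109. The smallest positive estimate that passes is 1.96 × 0.109 = 0.214, already above the true value.
- Chance of passing ≈ 1 − Φ(1.96 − 0.20/0.109) = 1 − Φ(0.127) = 0.45.
- Mean estimate when kept ≈ 0.20 + 0.109 × φ(0.127)/0.45 = 0.20 + 0.109 × 0.396/0.45 = 0.296.
- Ratio to truth: 0.296/0.20 = 1.48. Simulation gives 1.47.

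**Simulation, n = 84, a = 0.25.** Ratio is the mean a × b among kept runs divided by the true a × b.

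| True b (SD) | Kept, b path only | Ratio | Kept, both paths | Ratio |
|---|---|---|---|---|
| 0.15 | 28% | 1.90 | 18% | 2.34 |
| 0.20 | 45% | 1.47 | 29% | 1.82 |
| 0.25 | 64% | 1.26 | 41% | 1.56 |
| 0.30 | 80% | 1.12 | 51% | 1.39 |

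The two halves agree with each other. The a path at 0.25 passes about 64% of the time, so at b = 0.20 both pass in 0.64 × 0.45 = 29%. Selection on a adds a factor of about 1.82/1.47 = 1.24, and 1.12 × 1.24 = 1.39 at b = 0.30. With no screen the ratio is about 1.00. At b = 0.40 the one-path ratio falls to 1.01 to 1.02.

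**Second setup: six candidates, one real, survivors refitted jointly, n = 84.** Ranges cover residual correlation of 0.3 and 0 between mediators.

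| True a = b | Ratio, b path only | Ratio, both paths |
|---|---|---|
| 0.14 | 1.8–1.9 | about 4.0 |
| 0.20 | 1.3–1.45 | about 2.2 |
| 0.30 | 1.04–1.13 | about 1.3 |
| 0.39 | 0.94–1.02 | about 1.05 |

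At n = 100 and a = b = 0.2 the ratios are 1.3 and 1.9.

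**No real mediator.** If the tests are independent, the chance that at least one of six passes a b-path screen is 1 − 0.95⁶ = 26.5%. For seven it is 1 − 0.95⁷ = 30.2%.

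**Without the screen.** With all six mediators kept in the model (correlation 0.3), the mean estimated and true indirect effects are 0.0195 and 0.0196, 0.040 and 0.040, 0.089 and 0.090, and 0.151 and 0.152, for a = b of 0.14, 0.2, 0.3 and 0.39.

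**The case against.** Aim 4 is exploratory, the effect sizes above are assumed, and the simulations simplify a mixed model with weekly pain scores. All three points stand, and they limit the weight of the finding. The third limits it least: the mediators are measured only twice, so weekly pain scores add little information on how mediator change differs between people.

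A reader might infer more than the documents support, in three ways.

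- *That H5 as a whole would be settled by chance selection.* It would not. Aims 1, 2 and 3 model cumulative THC and CBD dose against pain, cytokines and psychological symptoms with no mediator screen. The Aim 4 total effect does not depend on mediator choice either. Only the mediator-pain link and the product term are exposed.
- *That non-significant mediators vanish from the report.* The plan says which mediators enter the final model, and that the first-stage analysis is run for each candidate. It does not say those results will be withheld. What is missing is a commitment to report them.
- *That every reported effect is too large.* The bias is conditional on selection and fades as effects grow. With correlated mediators and large paths, the one-path ratio can fall slightly below 1. If dropped mediators were counted as zero, the average would be too small: 0.28 × 1.90 = 0.53 of the truth at b = 0.15, and 0.80 × 1.12 = 0.90 at b = 0.30.

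**Conclusion.** The point holds in a limited form. The selection rule is explicit, selection and estimation share the same participants, and nothing elsewhere in the documents offsets it. Conditional on selection, indirect effects built on small-to-moderate paths are biased away from zero, and intervals that ignore the screen are invalid.

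Under the single-mediator assumptions, the overstatement for b from 0.15 to 0.30 SD runs from about 90% down to 12% with a one-path screen, and from about 134% down to 39% if both paths are tested. Which range applies cannot be settled from the plan. The one-path bias is negligible for large mediator-pain effects. This is an inexpensive improvement to an exploratory aim; the primary analysis is untouched.

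**What to change.** In section 7.A, Aim 4:

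1. Delete the significance screen.
2. Fix the mediator set in advance: TNF-α, IL-6, IL-4, IL-10, CES-D and GAD-7. State whether IL-1β (listed in section 2.C) and psychotic symptoms (named in section 1.A) are included.
3. Estimate each indirect effect singly and in one joint model. Report all of them with participant-level bootstrap 95% intervals regardless of significance, labelled exploratory.
4. State the number of intervals. Six mediators × two dose exposures × two models gives 24.
5. If a screen is kept, state the path tested and the level, and repeat the screen inside each bootstrap resample.

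No new data are needed. The cost is SAP wording, wider intervals in the joint model and modest extra programming, including a decision on how the bootstrap combines with the planned multiple imputation. The change removes the selection bias but not the low power: a weak mediator would appear as an interval that includes zero.
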